10.9.8 Hepatotoxicity

Serious cases of hepatotoxicity, including fatal outcomes, have occurred in patients receiving ADCETRIS. Cases were consistent with hepatocellular injury, including elevations of transaminases and/or bilirubin. Cases have occurred after the first dose of ADCETRIS or after ADCETRIS rechallenge. Preexisting liver disease, elevated baseline liver enzymes, and concomitant medications may also increase the risk. Monitor liver enzymes and bilirubin.

Patients experiencing new, worsening, or recurrent hepatotoxicity may require a delay, change in dose, or discontinuation of ADCETRIS.

10.9.9 Progressive Multifocal Leukoencephalopathy

JC virus infection resulting in PML and death has been reported in ADCETRIS-treated patients. In addition to ADCETRIS therapy, other possible contributory factors include prior therapies and underlying disease that may cause immunosuppression. Consider the diagnosis of PML in any patient presenting with new-onset signs and symptoms of central nervous system abnormalities.

Hold ADCETRIS dosing for any suspected case of PML and discontinue ADCETRIS dosing if a diagnosis of PML is confirmed.

10.9.10 Pulmonary Toxicity

Pulmonary toxicity has been reported in patients receiving ADCETRIS. A causal association with single-agent ADCETRIS has not been established. In the event of new or worsening pulmonary symptoms (e.g., cough, dyspnea), perform a prompt diagnostic evaluation and institute appropriate medical therapy.

10.9.11 Serious Dermatologic Reactions

Stevens-Johnson syndrome (SJS) and toxic epidermal necrolysis (TEN), including fatal outcomes, have been reported with ADCETRIS. If SJS or TEN occurs, discontinue ADCETRIS and administer appropriate medical therapy.

10.9.12 Embryo-Fetal Toxicity

There are no adequate and well-controlled studies of ADCETRIS in pregnant women. However, based on its mechanism of action and findings in animals, ADCETRIS can cause fetal harm when administered to a pregnant woman. Brentuximab vedotin caused embryo-fetal toxicities, including significantly decreased embryo viability and fetal malformations, in animals at maternal exposures that were similar to human exposures at the recommended doses for patients with HL and sALCL. If this drug is used during pregnancy, or if the patient becomes pregnant while receiving the drug, the patient should be apprised of the potential hazard to the fetus.

11. ADVERSE EVENTS

11.1 Definitions of Adverse Events

11.1.1 Adverse Event (AE)

An **adverse event** is defined as any untoward medical occurrence associated with the use of a drug in humans, whether or not considered drug related. An adverse event (also referred to as an adverse experience) can be any unfavorable and unintended sign (e.g. an abnormal laboratory finding), symptom, or disease temporarily associated with the use of a drug, without any judgment about causality. An adverse event can arise with any use of the drug (e.g., off-label use, use in combination with another drug) and with any route of administration, formulation, or dose, including an overdose. Adverse events will be graded according to the NCI Common Toxicity Criteria, Version 4.0 (Appendix I).

11.1.2 Suspected Adverse Reaction (SAR)

Suspected adverse reaction is any adverse event for which there is a reasonable possibility that the drug caused the adverse event. For the purposes of IND safety reporting, ‘reasonable possibility’ means there is evidence to suggest a causal relationship between the drug and the adverse event. A suspected adverse reaction implies a lesser degree of certainty about causality than adverse reaction, which means any adverse event caused by a drug. Suspected adverse reactions are the subset of all adverse events for which there is a reasonable possibility that the drug caused the event.

Examples of types of evidence that would suggest a causal relationship between the drug and the adverse event:

- A single occurrence of an event that is uncommon and known to be strongly associated with drug exposure (e.g., angioedema, hepatic injury, Stevens-Johnson Syndrome).
- One or more occurrences of an event that is not commonly associated with drug exposure, but is otherwise uncommon in the population exposed to the drug (e.g., tendon rupture).
- An aggregate analysis of specific events observed in a clinical trial (such as known consequences of the underlying disease or condition under investigation or other events that commonly occur in the study population independent of drug therapy) that indicates those events occur more frequently in the drug treatment group than in a concurrent or historical control group.

11.1.3 Adverse Reaction (AR)

An adverse reaction is any adverse event caused by a drug. Adverse reactions are a subset of all suspected adverse reactions where there is reason to conclude that the drug caused the event.

11.1.4 Serious Adverse Event (SAE)

An adverse event or suspected adverse reaction is considered “serious” if it results in any of the following outcomes:

- Results in death
 - Is life-threatening. Life-threatening is defined as an adverse event or suspected adverse reaction that places the subject at immediate risk of death. It does not include an adverse event or suspected adverse reaction that, had it occurred in a more severe form, might have caused death.
 - Requires inpatient hospitalization or prolongation of existing hospitalization
- NOTE: Hospitalizations that are not considered SAEs are:
- Hospitalization planned prior to first administration of study drug
 - Hospitalization for elective treatment of a pre-existing condition unrelated to the study medication
- Results in persistent or significant disability/incapacity

- Is a congenital anomaly or birth defect
- Is an important medical event (defined as a medical event(s) that may not be immediately life-threatening or result in death or hospitalization but, based upon appropriate medical and scientific judgment, may jeopardize the patient or may require intervention (e.g., medical, surgical) to prevent one of the other serious outcomes listed in the definition above). Examples of such events include, but are not limited to, intensive treatment in an emergency room or at home for allergic bronchospasm; blood dyscrasias or convulsions not resulting in hospitalization; or the development of drug dependency or drug abuse.

Pregnancy

- Pregnancy of a patient or of the female partner of a male patient during the study or within 30 days after the last dose of study drug should be reported via an SAE report. Should pregnancy occur in a female participant during the treatment period, study drug should be discontinued and Seattle Genetics notified immediately. Should a pregnancy occur in a female companion of a male participant during the treatment period, the male participant can continue treatment and Seattle Genetics notified immediately. Any such pregnancy is to be followed until final outcome.

11.1.5 Unexpected Adverse Event

An adverse event or suspected adverse reaction is considered “unexpected” if it is not listed in the investigator brochure or is not listed at the specificity or severity that has been observed; or, if an investigator brochure is not required or available, is not consistent with the risk information described in the general investigational plan or elsewhere in the current application, as amended. For example, under this definition, hepatic necrosis would be unexpected (by virtue of greater severity) if the investigator brochure referred only to elevated hepatic enzymes or hepatitis. Similarly, cerebral thromboembolism and cerebral vasculitis would be unexpected (by virtue of greater specificity) if the investigator brochure listed only cerebral vascular accidents. “Unexpected,” as used in this definition, also refers to adverse events or suspected adverse reactions that are mentioned in the investigator brochure as occurring with a class of drugs or as anticipated from the pharmacological properties of the drug, but are not specifically mentioned as occurring with the particular drug under investigation.

This definition relies entirely on the adverse events or suspected adverse reactions listed in the investigator brochure for the particular drug under investigation (or elsewhere in the general investigational plan if an investigator brochure is not required or available) as the basis for determining whether newly acquired information generated from clinical trials or reported from other sources is *unexpected*. This means that events not listed for the particular drug under investigation in the investigator brochure are considered “unexpected” and those listed are considered “expected.” When new adverse event information is

received, it is the sponsor's responsibility to determine whether the event is "unexpected" for IND safety reporting purposes. In the clinical trial setting, there has been some confusion with the term "expected" as it has been used to mean "anticipated" for the disease being treated or population being studied rather than "listed in the investigator brochure." For example, some adverse events can be anticipated to occur as a result of a disease or in an older population (e.g., cancer-related deaths in a cancer trial, strokes or acute myocardial infarctions in an older population). However, for reporting purposes, these anticipated events are not "expected" because they are not listed in the investigator brochure (i.e., the test drug is not suspected or known to cause them).

Adverse events listed in the investigator brochure as occurring with members of the same class of drugs, or as anticipated from the pharmacological properties of the drug, would be considered *unexpected* until they have been observed with the drug under investigation. For example, although angioedema is anticipated to occur in some patients exposed to drugs in the angiotensin-converting enzyme (ACE) inhibitor class and angioedema would be described in the investigator brochure as a class effect, a case of angioedema observed with the drug under investigation should be considered *unexpected* for reporting purposes until it is included in the investigator brochure as occurring with the drug under investigation.

11.1.6 Determining Attribution to the Investigational Agent(s)

Attribution: An assessment of the relationship between the AE and the medical intervention. CTCAE does not define an AE as necessarily "*caused by a therapeutic intervention*". After naming and grading the event, the clinical investigator must assign an attribution to the AE using the following attribution categories:

Relationship	Attribution	Description
Unrelated to investigational agent/intervention	Unrelated	The AE is clearly NOT related
	Unlikely	The AE is doubtfully related
Related to investigational agent/intervention	Possible	The AE may be related
	Probable	The AE is likely related
	Definite	The AE is clearly related

11.2 Adverse Event (AE) Reporting Requirements:

Adverse events (AEs) will be recorded from the time of first study drug administration and for at least 30 days after treatment discontinuation, regardless of whether or not the event(s) are considered related to trial medications. AEs occurring after the post-treatment safety assessment visit can be collected by telephone or other means of communication. All AEs considered related to trial

medication will be followed until resolution, return to baseline, or deemed clinically insignificant, even if this occurs post-trial.

11.2.1 Participating Site Reporting Responsibilities

11.2.1.1 Reporting to the IU Simon Cancer Center

Any serious adverse event or unanticipated problem occurring within 30 days of the last dose of study drug must be reported to the IU Simon Cancer Center within **1 business day** of notification or discovery of the incident, using the MedWatch Form 3500A (Mandatory Reporting). SAEs that occur greater than 30 days from last dose of study drug must be reported to the IU Simon Cancer Center if the event is possibly, probably, or definitely related to the study drug. This form must be accompanied by a cover letter which: identifies the event, is signed by the local principal investigator or treating physician, includes the applicable study number and title, and contains the following:

- Site assessment of the event attribution to investigational product or study procedure
- Site assessment of event expectedness (expected vs. unexpected)
- Assessment of whether or not the research places subjects at a greater risk of harm than was previously known or recognized
- Assessment of the event's affect on the risk to benefit ratio
- Statement as to whether the informed consent statement should reflect changes in the potential risks involved
- Statement as to whether the event has been reported previously, and if so, whether the frequency is considered unusually high

Send to: IUSCC Clinical Trials Office
 ATTN: Multicenter coordinator/ IUSCC-0568
 [contact]
 E-mail: [contact]

The Multicenter Network Associate Administrator, or designee, will distribute the reports to all participating sites, the FDA and to Seattle Genetics as per section 11.2.2 below. Copies of all serious adverse event reports or unanticipated problems reports will be kept on file in the IU Simon Cancer Center Clinical Trials Office.

11.2.1.2 Reporting to the IRB

Each participating site will report adverse events and unanticipated problems to their IRB per local guidelines. Any event that requires expedited reporting to the local IRB will also be submitted to the IU Simon Cancer Center for distribution to the Funder.

11.2.2 Coordinating Center Reporting Responsibilities

In addition to the responsibilities above, the Coordinating Center will also be responsible for reporting events to the Funder and the FDA.

11.2.2.1 Reporting to Seattle Genetics

SAEs

IUSCC will report to Seattle Genetics all SAEs that are sent to the FDA at the time of submission to the FDA. Follow-up information will be provided to Seattle Genetics as reasonably requested. Send SAE reports on the MedWatch Report Form to:

Seattle Genetics Drug Safety

[contact] or [contact]

Email: [contact]

A study-specific cumulative SAE line listing of all SAEs with assessment of causality to investigational product will be sent **monthly** to [contact].

Study Initiation

IUSCC will provide the following to Seattle Genetics prior to initiation of Seattle Genetics support (provision of Product and/or funding):

- Final study protocol
- Fully executed IST Agreement
- Regulatory Response Documentation (IND or CTA documentation if applicable)
- IRB/IEC approval

Study Maintenance

Throughout the study, IUSCC will provide the following to Seattle Genetics:

- At least one safety study status update per year, to include information on enrollment and study completion dates.
- Notification of any amendment to the original protocol after the research has begun; and *immediate* notification of any amendments made due to safety reasons.

Study Closure

IUSCC will provide Seattle Genetics a copy of the IND Annual Report. Upon study closure, IUSCC will certify that all safety reporting obligations were met.

11.2.2.2 Reporting to the FDA

Per CFR 312.32 (c), the sponsor-investigator of the IND ([name]) must notify the Food and Drug Administration (FDA) and all participating investigators in a written IND safety report of any adverse experience that meets the criteria outlined below. There are two types of reports to the FDA: 7-day and 15-day reports.

7-Day Reports:

The investigator-sponsor of the IND must notify the FDA and all participating investigators in a written IND safety report of any adverse experience:

- **fatal or life-threatening experience** that is ***both***
- **suspected to be associated with use of the drug *and***
- **unexpected (as defined in 11.1.5)**

The FDA will be notified as soon as possible but no later than **7 calendar** days after the investigator-sponsor's initial receipt of the information.

15-Day IND Reports:

The investigator-sponsor of the IND must notify the FDA and all participating investigators in a written IND safety report of any adverse experience:

- **suspected to be associated with use of the drug** that is ***both***
- **serious** ***and***
- **unexpected** (as defined in 11.1.5)

The FDA will be notified as soon as possible but no later than **15 calendar** days after the investigator-sponsor's initial receipt of the information.

Report Content:

Each written notification may be submitted on FDA Form 3500A or in a narrative format and must bear prominent identification of its contents, i.e., "IND Safety Report". For purposes of this protocol, the **MedWatch Report Form (FDA 3500A mandatory reporting), along with FDA Form 1571, and a cover letter** submitted to the appropriate FDA division, will serve as the written IND safety report. Follow-up information to a safety report should be submitted as soon as the relevant information is available. Submit to the FDA:

- MedWatch Report Form (FDA 3500A)
- FDA Form 1571
- Cover Letter

Notify the FDA via phone or fax using MedWatch 3500A (mandatory reporting form)

- [contact], option #1
- Fax: [name]

The IUSCC Protocol Development Coordinator should be contacted to assist with all FDA submissions and will be provided with a copy of all events that are reported to the FDA. All IND submissions will be maintained in a master file in the Clinical Trials Office of the IU Simon Cancer Center.

11.2.2.3 Reporting to Participating Sites

Seattle Genetics will send IND safety reports from external studies that involve the study drug to the Multicenter Network Associate Administrator, or designee. The Multicenter Network Associate Administrator, or designee, will forward the safety reports to the sponsor-investigator, or designee, who will review these reports and determine if revisions are needed to the protocol or consent. IUSCC will forward these reports to participating sites every 2 weeks.

For IND safety reports originating from this study, IUSCC will distribute reports which are serious, unexpected and associated with the study intervention (possibly, probably or definitely related) to all participating sites in the form of an Expedited Safety Report (external safety/IND safety report) within 15 calendar days from determination that the suspected adverse reaction qualifies for reporting. Copies of these External Safety Reports will be kept on file in the IU Simon Cancer Center

Clinical Trials Office. Upon receipt from IUSCC, site investigators, or designees, are responsible for submitting these safety reports to their respective IRBs, as per their IRB policies.

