5.2.1 Dose and Administration

Brentuximab vedotin, 1.8 mg/kg (1.2 mg/kg in patients with grade 2 peripheral neuropathy at enrollment) will be administered by IV infusion given over approximately 30 minutes on Day 1 of each 21-day cycle. In the absence of infusion-related reactions, the infusion rate for all patients should be calculated in order to achieve a 30-minute infusion period. If an infusion reaction does occur, infusion rates should be adjusted as necessary and documented appropriately in source documents. Brentuximab vedotin must

not be administered as an IV push or bolus. Brentuximab vedotin should not be mixed with other medications.

Dosing is based on patient weight according to the institutional standard; however, doses will be adjusted for patients who experience a $\geq 10\%$ change in weight from baseline. Actual weight will be used except for patients weighing greater than 100 kg; dose will be calculated based on 100 kg for these individuals. Rounding is permissible within 5% of the nominal dose.

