7. STUDY CALENDAR & EVALUATIONS

Procedure	Screening ¹ (≤ 28 days before 1 st dose)	Every Cycle (21 days ± 3 days)	Before cycle 3 & cycle 5	Before cycle 9 & then after every 4 cycles	Post Treatment Safety Assessments ⁶	Follow-Up ¹⁰
Informed consent and medical history	X					
Patient Registration	X					
Brentuximab vedotin administration ²		X				
ECOG Performance Status	X	X			X	
Physical exam ³ , vital signs	X	X			X	
Serum AFP and beta-hCG	X	X			X	X ¹²
CBC (differential & platelets)	X	X ^{4,11}			X	
Complete metabolic panel	X	X ⁴			X	
Magnesium and phosphorus	X	X ⁴			X	
Pregnancy test ⁵	X	X			X	
Concomitant medications	X	X			X	
Adverse event monitoring ⁷		X			X	
Radiologic evaluations ⁸	X		X	X		X ¹²
Archival tissue ⁹	X					
Survival						X

Footnotes:

- 1 All procedures are to be performed ≤ 28 days prior to study drug administration. Screening assessments may be used in place of the Cycle 1 Day 1 assessments if performed within 7 days prior to the Day 1 visit. Standard of care procedures may be used for screening requirements if performed within 28 days prior to study drug administration.
- 2 Brentuximab vedotin is administered on Day 1 of each Cycle. First dose must be administered within 7 days of registration.
- 3 Complete physical exam to be performed within 28 days of first study drug administration (for screening requirements), Day 1 Cycle 1 and at Final Safety Follow-up. At other time-points, a brief symptom-directed exam and ECOG performance evaluation are sufficient. At Screening, height is recorded and body surface area (BSA) calculated
- 4 Hematologic and chemistry parameters (including serum creatinine, AST, ALT, BUN, phosphate, bilirubin, calcium & magnesium) to be performed on Day -3 to Day 1 of every cycle.
- 5 Females of childbearing potential only. Pregnancy tests must be serum at screening and the post treatment safety assessment visit. Urine pregnancy tests are required on Day 1 of each Cycle. A positive urine pregnancy test must be confirmed by a serum pregnancy test and a pelvic US since some NSGCT can secrete beta-hCG. A pelvic US does not need to be repeated with each cycle unless the treating physician thinks it is necessary to do so.
- 6 The post-treatment safety assessment will be done 21 ± 7 days after the last dose of study drug.

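### For fatal or life-threatening unexpected reactions the 7-day limit binds notice to the FDA only; sites may be told up to 15 days after a later determination

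*Combined protocol and SAP*

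**What the plan says.** Section 11.2.2.2 (Reporting to the FDA) describes two kinds of report. Under the 7-day heading, for events that are fatal or life-threatening, suspected to be drug-associated and unexpected, the investigator-sponsor "must notify the FDA and all participating investigators in a written IND safety report of any adverse experience". The duty therefore names two addressees. The deadline names one: "The FDA will be notified as soon as possible but no later than" 7 calendar days, counted from the investigator-sponsor's initial receipt.

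Section 11.2.2.3 (Reporting to Participating Sites) sets the timetable for sites. For reportable events in the trial itself, "IUSCC will distribute reports which are serious, unexpected and associated with the study intervention (possibly, probably or definitely related) to all participating sites", and this is to happen "within 15 calendar days from determination that the suspected adverse reaction qualifies for reporting".

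Section 11.2.1.1 covers the inbound leg: an SAE "must be reported to the IU Simon Cancer Center within 1 business day of notification or discovery of the incident". It then leaves onward distribution to sites, the FDA and the drug supplier to section 11.2.2. Section 11.2.2.1 says that the supplier receives SAEs that go to the FDA when they are submitted to the FDA.

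**The concern.** The site rule in 11.2.2.3 differs from the FDA rule in two ways: it is longer (15 days against 7), and its clock starts later (determination against receipt). It also has no separate tier, so a death on study falls under the same site deadline as any other serious, unexpected, related event. The regulator, and through 11.2.2.1 the supplier, work to the 7-day clock. The investigators who give the drug do not.

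This matters because the treating investigators are the people who can act before the next infusion. Section 13.2.1 lets a site investigator deviate from the protocol to remove an immediate hazard, but that power is of use only to someone who knows of the hazard. With dosing every three weeks, a notice interval of 15 days or more covers most of a cycle.

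**Working it through.** **Does the 15-day site rule cover the 7-day events?** Section 11.1.4 counts death and life-threatening events as serious. The 7-day class is also suspected and unexpected. Section 11.2.2.3 covers serious, unexpected events that are possibly, probably or definitely related. The 7-day class therefore lies inside the 15-day site rule, and nothing in 11.2.2.3 takes it out.

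**Inputs**
- Cycle length C = 21 days (5.2.1: "on Day 1 of each 21-day cycle"). The calendar in section 7 allows a window of 3 days either way, so C runs from 18 to 24.
- FDA limit: 7 days from receipt (11.2.2.2).
- Site limit: 15 days from determination (11.2.2.3).
- t = days from receipt to determination. Section 11.2.2.3 sets no limit on it. A 7-day FDA report already requires the event to be judged suspected and unexpected, so t is taken as 0 to 7.
- Assumption not in the documents: next doses fall evenly over the cycle.

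The plan gives no figure of its own for this, so there is none to reproduce.

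**Formulas.** Latest site notice D = t + 15 days after receipt. Lag behind the FDA limit = D − 7 = t + 8. Share of continuing patients due a dose before notice = min(1, D/C).

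**Results**

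| Latest notice to sites | C = 18 | C = 21 | C = 24 |
|---|---|---|---|
| Day 7 (FDA limit applied to sites) | 7/18 = 39% | 7/21 = 33% | 7/24 = 29% |
| Day 15 (t = 0) | 15/18 = 83% | 15/21 = 71% | 15/24 = 62.5% |
| Day 22 (t = 7) | 100% | 100% | 22/24 = 92% |

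The lag is 8 days at t = 0 and 15 days at t = 7. At t = 0 and C = 21 the extra 8 days cover 8/21 = 38% of a cycle.

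**Could another route inform sites sooner?** Section 13.1.2 schedules calls with sites at least monthly, and section 13.1.3 has the DSMB meet once a year. Suppose a call falls at a random time within 30 days and always conveys the event. With m the smaller of D and 21, the share becomes (m − m²/60)/21:
- D = 15: (15 − 3.75)/21 = 54%
- D = 22, so m = 21: (21 − 7.35)/21 = 65%

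The calls reduce the share but do not guarantee earlier notice.

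**Allowing for patients who stop treatment.** Section 1.2 cites a median PFS of 4 weeks on earlier single agents, and section 6.2 ends treatment at progression. As an illustration, take exponential time on treatment with a 28-day median, so λ = ln 2/28 = 0.0248 per day. The share of those on treatment at receipt who are redosed by day D is (1 − e^(−λD))/(21λ):
- D = 15: 60%
- D = 7: 31%
- difference: 29%

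**Head count under the same assumption.** Accrual of 2 + 1 = 3 patients a month (12.3) and a mean of 28/ln 2 = 40 days on treatment give about 4 patients on treatment at once. The extra 8 days then affect about 4 × 0.29 ≈ 1 patient. With a median of 8 weeks, about 8 are on treatment and 2 to 3 are affected.

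**The case against.** The strongest reply is that 11.2.2.2 describes one report with two addressees under a 7-day heading, and that 11.2.1.1 has one office distribute to sites, FDA and supplier. On that reading everyone receives the report together, and the 15 days in 11.2.2.3 are only an outer limit. This may well be the intent, and sites may in practice hear at once. But 11.2.1.1 defers to 11.2.2, the 7-day sentence limits the FDA only, and 11.2.2.3 is the only place that gives sites a date. If 7 days was meant for both, the sections conflict and need reconciling; if it was not, the gap is real.

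A reader might go further and infer that most patients on treatment would be redosed before their investigator hears of a death. The documents do not support that. The percentages describe the last permitted day, rest on an assumed even spread of doses, and concern only continuing patients at sites that depend on the notice. The reporting site and the coordinating centre already know, and the split of patients by site is not given. At t = 0, more than half of all on-treatment patients would be affected only if more than 0.5/(15/21) = 70% of them were at dependent sites. The head count is also small, as the illustration shows.

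Other protections exist as well. Calls can be held more often as needed (13.1.2), and under the same section investigators may recommend early closure at any time and the DSMC may suspend the study. These are discretionary and do not set a deadline for informing sites.

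A reader might also conclude that counting 15 days from determination is deficient for the other serious, unexpected, related events. That is a separate question. It is not quantified here, and the regulation that 11.2.2.2 cites is not among the documents, so no claim of non-compliance can be made.

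**Conclusion.** The point holds as a gap between two sections of the safety-reporting plan. For fatal or life-threatening, suspected, unexpected reactions the FDA must be told within 7 days of receipt, while the only dated site rule allows 15 days from a determination that may come later. The site deadline can therefore fall 8 to 15 days after the FDA's, provided the determination is made within the FDA's own 7 days.

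With determination on the day of receipt, the share of continuing patients at dependent sites due a dose before notice is at most 71% (62.5% to 83% for 24- to 18-day cycles), against 33% under a 7-day limit. A later determination raises that ceiling; earlier notice, or patients stopping treatment, lowers the actual share. Even a 7-day limit would leave about a third due a dose first.

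No endpoint, analysis or decision rule is affected. The case for change is that the improvement is relevant to safety and costs very little.

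**What to change.** Reconcile 11.2.2.2 and 11.2.2.3 by adding one sentence to 11.2.2.3, for example: *A report that meets the 7-day criteria in 11.2.2.2 is sent to all participating sites at the same time as to the FDA, and at the latest 7 calendar days after the sponsor-investigator first receives the information.* This gives sites the simultaneous notice that 11.2.2.1 already gives the drug supplier. The 15-day rule for all other reports can stay as it is.

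The cost is an earlier e-mail of a report already being prepared for the FDA. The drawback is that the first report to sites may be less complete; 11.2.2.2 already provides for follow-up information. No dose or treatment rule changes.
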